### Open-label treatment phase/extension period

For summarization of data including, but not limited to, adverse events, medications, non-drug therapies/procedures, protocol deviations and relapses, data occurring from Study Day 1 through the Month 18 interim analysis data cut-off will be considered as part of the open-label treatment phase. Data occurring post Month 18 interim analysis data cut-off will be considered as part of the open-label extension period.

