**Table 2 Month 18 interim analysis data cut-off for different participant scenarios**

Participant scenario	Cut-off	Participant data included in Month 18 interim analysis (primary analysis)
Completed Month 18 visit	Date of Month 18 visit + 7 days (inclusive)	All available data up to the date of the Month 18 visit + 7 days (inclusive)*
Did not complete Month 18 visit		
Discontinued study prior to Month 18 visit	None	All available data
Did not discontinue study prior to Month 18 visit	Date of next scheduled visit after Month 18 (exclusive)	All available data up to the date of the next scheduled visit (including home visit) after Month 18 (exclusive).** If the next scheduled visit after Month 18 has not been completed, all available data is used.

\* Including data such as adverse events, medications, non-drug therapies/procedures, protocol deviations and relapses that started prior to or on the date of the Month 18 visit + 7 days.

\*\* Including data such as adverse events, medications, non-drug therapies/procedures, protocol deviations and relapses that started prior to the date of the next scheduled visit (including home visit) after Month 18.

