## Open-label treatment phase duration

Open-label treatment phase duration in days will be calculated as follows:

- [(date of Month 18 interim analysis data cut-off – date of first dose of ofatumumab) + 1] for ofatumumab-treated participants
- [(date of Month 18 interim analysis data cut-off – date of Week 0 visit) + 1] for healthy control participants

For participants who do not complete the Month 18 visit, the date of last contact/EOS will be used.

Study duration and open-label treatment phase duration will be summarized descriptively as continuous variables by Cohort using the SAF or HCAS, as appropriate.

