### **2.7.1.1 Adverse events of special interest / grouping of AEs**

The number and percentage of participants with at least one treatment-emergent AE in each of the following categories will be presented for the open-label treatment phase, open-label extension period and overall using the SAF:

- Injection site reaction
- Injection systemic reaction

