#### 5.6 Ofatumumab dose dates during open-label treatment phase and open-label extension period

The date of the last dose of ofatumumab during the open-label treatment phase and the date of the first dose of ofatumumab during the open-label extension period will be determined according to the following three participant scenarios.

1. Completed Month 18 visit and continued into open-label extension period
  - a. Last dose date of ofatumumab during open-label treatment phase is last dose date < Month 18 visit date
  - b. First dose date of ofatumumab during open-label extension period is first dose date  $\geq$  Month 18 visit date
2. Completed Month 18 visit and did not continue into open-label extension period
  - a. Last dose date of ofatumumab during open-label treatment phase is last dose date  $\leq$  Month 18 visit date
3. Did not complete Month 18 visit
  - a. Last dose date of ofatumumab during open-label treatment phase is last dose date  $\leq$  Month 18 interim analysis data cut-off date
  - b. First dose date of ofatumumab during open-label extension period is first dose date > Month 18 interim analysis data cut-off date

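### Around Month 18 the SAP assigns events and doses to phases by different dates, so early events after the first extension dose fall in the treatment phase; phase duration can also exceed study duration by up to 7 days

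*SAP*

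**What the plan says.** **Events.** For relapses, deviations, procedures, medications and adverse events alike, the phase rule in SAP 2.1.1 (Open-label treatment phase/extension period) is this: "data occurring from Study Day 1 through the Month 18 interim analysis data cut-off will be considered as part of the open-label treatment phase". It adds: "Data occurring post Month 18 interim analysis data cut-off will be considered as part of the open-label extension period". For Month 18 completers, Table 2 sets the cut-off at the visit date plus 7 days, inclusive. Its footnote brings in the same event types, down to "relapses that started prior to or on the date of the Month 18 visit + 7 days".

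**Doses.** SAP 5.6 uses another date for participants who completed Month 18 and continued (scenario 1): "Last dose date of ofatumumab during open-label treatment phase is last dose date < Month 18 visit date". For the other side of the split, "First dose date of ofatumumab during open-label extension period is first dose date" on or after that visit date. Completers who do not continue (scenario 2) keep a visit-day dose in the treatment phase. For those who missed the Month 18 visit (scenario 3), doses are split at the data cut-off itself.

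**Where these dates are used.** SAP 2.4.1 computes exposure within each phase from the SAP 5.6 dose dates. SAP 2.7.1 tabulates adverse events by phase. SAP 2.7.1.1 does the same for injection site and injection systemic reactions, which "will be presented for the open-label treatment phase, open-label extension period and overall using the SAF".

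**Durations.** Under SAP 2.4.1, study duration ends at last contact/EOS, while treatment-phase duration ends at the Month 18 cut-off. The only exception is: "For participants who do not complete the Month 18 visit, the date of last contact/EOS will be used".

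**A competing cut-off.** SAP 2.13 says the Month 18 outputs hold data up to and including the visit date, with no added days.

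**The concern.** A by-phase safety table is read on the assumption that an event and the dose before it sit in the same column. For continuers that can fail at Month 18. Protocol Table 6-5 lists Month 18 as the first extension dose, and Protocol 6.3.2 asks that a dose on a visit day follow the visit assessments. A reaction that evening, or during the following week, goes into the treatment-phase column, while the injection counts as extension exposure. Injection reactions are the category most closely tied to a single dose, and they have their own by-phase table.

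The duration rule has a separate fault. A phase that is part of the study should not last longer than the study, yet for some Month 18 completers the formulas give that result.

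At stake are the by-phase descriptive safety tables and one descriptive duration summary.

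**Working it through.** The plan gives no figure on this point, so the check applies its date rules side by side.

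**Events against doses, continuers only (SAP 5.6 scenario 1).** Take the Month 18 visit as day 0.

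- Dose rule (SAP 5.6): extension if dose day ≥ 0, otherwise treatment phase.
- Event rule (SAP 2.1.1 and Table 2): treatment phase if onset day ≤ 7, otherwise extension.

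A first extension dose on day k and a later event on day a fall in different phases when 0 ≤ k ≤ a ≤ 7. For a given k that is 8 − k onset days:

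| Dose day k | 0 | 1 | 2 | 3 | 4 | 5 | 6 | 7 | 8 or later |
|---|---|---|---|---|---|---|---|---|---|
| Onset days placed in the other phase | 8 | 7 | 6 | 5 | 4 | 3 | 2 | 1 | 0 |

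The rules overlap on 8 calendar days (day 0 to day 7), giving 8 + 7 + … + 1 = 36 mismatched dose/onset combinations. These are combinations of dates, not events.

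**How ordinary the overlap is.** Protocol Table 8-1 allows the Month 18 visit ±3 days around Day 540. Protocol 6.3.2 gives ±3 days for monthly doses that follow a missed one. Assume that both the visit and the dose keep to Days 537–543; this is my reading of the windows.

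- Dose minus visit then runs from 537 − 543 = −6 to 543 − 537 = +6 days.
- Of the 7 × 7 = 49 day pairs, 28 put the dose on or after the visit, and all 28 lie inside the overlap.
- The other 21 put the dose before the visit, where SAP 5.6 counts it in the treatment phase and no split arises.

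**Under the SAP 2.13 cut-off.** The event rule becomes onset day ≤ 0. Only k = 0 with a = 0 remains, so 36 combinations fall to 1. Adopting SAP 2.13 would shrink the mismatch but not remove it.

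**Scenarios 2 and 3.** For completers who do not continue, a visit-day dose and the events of the next 7 days are both treatment phase. For those without a Month 18 visit, doses are split at the cut-off, as events are. Neither group has the problem.

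**Duration.**

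- Treatment-phase duration = cut-off date − Day 1 date + 1. With the visit on Study Day 540, the cut-off is Study Day 547 and the result is 547 days.
- Study duration = last contact/EOS date − Day 1 date + 1. If last contact is the Month 18 visit, the result is 540 days.
- Excess: 547 − 540 = 7 days, or 7/540 = 1.3%.
- If last contact is j days after the visit, the excess is 7 − j days for j = 0 to 7, and nil beyond that.

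The clearest case is a healthy control who ends at Month 18. Protocol 9.3 places EOS at Month 18 for those who do not continue, and SAP 1.1 gives healthy controls no safety evaluation afterwards.

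**After the fix below.** If continuers' events with onset on or after the first extension dose go to the extension, the 36 combinations fall to 0.

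**The case against.** Much can be said for leaving this alone.

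- **No statistic divides one by the other.** The by-phase tables in SAP 2.7.1 and 2.7.1.1 are numbers and percentages of participants. No exposure-adjusted event rate appears in the visible text. Exposure is last dose date minus first dose date plus 1, so for a continuer it already stops before the Month 18 visit while events go on counting. The 7 days do not cause that gap. This stands.
- **Few events are likely.** Protocol 4.5 describes systemic injection reactions in the pivotal trials as almost all mild to moderate and confined to the first injection. That suggests few at about the 21st dose, although it says nothing about site reactions. This stands as a reason to expect a small effect.
- **The 7 days are deliberate.** The SAP document history records them as a revision of the Month 18 cut-off. That supports keeping them for data capture. It does not explain why doses use a different date.
- **The duration excess is small and not universal.** Ofatumumab participants who do not continue may have up to 100 days of safety follow-up, and an MRI is allowed up to 7 days after the visit, so last contact may fall later. This limits the problem but does not help a healthy control last seen at Month 18.

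Stronger readings are tempting and are not supported. A reader might infer that the extension loses all reactions to its first dose, but only onsets up to day +7 move. A reader might also set 20 scheduled treatment-phase doses (Protocol Table 6-4) against reactions to 21, or call 1 of 13 extension doses (7.7%) the size of the error. Those are schedule counts that say nothing about how many events move. Nor does the SAP say that the 7 days exist only for MRI, so restricting them to MRI does not follow.

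**Conclusion.** The point holds in a limited form. For ofatumumab participants who complete Month 18, continue, and receive their first extension dose within 7 days of the visit, events starting between that dose and day +7 are placed in a different phase from the dose. No section reconciles the two dates. The overlap is 8 calendar days. The number of events cannot be derived from the documents and is probably small. Overall-period summaries do not change, and SAP 5.4 plans no hypothesis tests.

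The duration fault also holds: up to 7 days too long (547 against 540 at nominal timing) for any Month 18 completer whose last contact/EOS precedes the cut-off, notably healthy controls who end there.

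The date overlap follows from the SAP's wording alone. The statement that every in-window dose on or after the visit falls inside it rests on the assumed ±3 day windows. The 7-day maximum rests on last contact being the visit itself.

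**What to change.** 1. **Phase of events in continuers.** Where the first extension dose under SAP 5.6 falls on or before the Table 2 cut-off, assign the event data listed in SAP 2.1.1 with onset on or after that dose to the extension. On the dose day, use the onset time or the recorded relation to the injection, so that an event before the injection stays in the treatment phase. Where the first extension dose comes after the cut-off, keep the existing cut-off.
2. **What stays.** Leave visit + 7 days unchanged for participants who do not continue, so that reactions to a visit-day dose remain in the treatment phase. Keep it also for the Month 18 data capture, including MRI. Only the phase label of continuers' events changes.
3. **Phase duration.** Define it as min(cut-off, last contact/EOS) − Day 1 + 1.
4. **SAP 2.13.** Reconcile its visit-date cut-off with Table 2.

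The cost is SAP wording and one extra date derivation, with no new data. Treatment-phase event counts may fall slightly, and the Month 18 outputs should say how they show the few events that then carry the extension label. The change concerns analysis dates only and touches no dosing rule.

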##### Study day 1, study day and event duration

**Study Day 1** is defined as the date of the first dose of ofatumumab for ofatumumab-treated participants and the date of the Week 0 visit for healthy control participants.

For assessment/event dates on or after Study Day 1, the **study day of the assessment/event** will be calculated as follows:

- [(date of assessment/event – date of first dose of ofatumumab) + 1] for ofatumumab-treated participants
- [(date of assessment/event – date of Week 0 visit) + 1] for healthy control participants

For assessment/event dates prior to Study Day 1, the **study day of the assessment/event** will be calculated as follows:

- (date of assessment/event – date of first dose of ofatumumab) for ofatumumab-treated participants
- (date of assessment/event – date of Week 0 visit) for healthy control participants

The **duration of an event** in days will be calculated as follows:

- (event end date – event start date) + 1

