## Baseline

Unless otherwise specified, baseline will be derived as follows:

- For ofatumumab-treated participants, baseline is the last non-missing assessment, including unscheduled assessments, obtained prior to or on the date of the first dose of ofatumumab.
- For healthy control participants, baseline is the last non-missing assessment, including unscheduled assessments, obtained prior to or on the date of the Week 0 visit.

Unless otherwise specified, all assessments obtained after the date of the first dose of ofatumumab for ofatumumab-treated participants, or after the date of the Week 0 visit for healthy control participants, are considered post-baseline assessments.

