#### **2.7.4.3 Columbia-Suicide Severity Rating Scale (C-SSRS)**

The C-SSRS is a questionnaire that prospectively assesses suicidal ideation and suicidal behavior. The number and percentage of participants in the following categories will be presented by analysis period/study phase (all prior history, recent history, open-label treatment phase, open-label extension period and overall) using the SAF.

- Each of the 10 individual suicidal ideation and behavior categories (during the analysis period/study phase of interest)
- Any suicidal ideation (answer of ‘yes’ to at least 1 of the 5 suicidal ideation questions during the analysis period/study phase of interest)
- Any suicidal behavior (answer of ‘yes’ to at least 1 of the 5 suicidal behavior questions during the analysis period/study phase of interest)
- Any suicidal ideation or behavior (answer of ‘yes’ to at least 1 of the 10 suicidal ideation and behavior questions during the analysis period/study phase of interest)
- Non-suicidal self-injurious behavior (during the analysis period/study phase of interest)

The analysis period ‘All prior history’ includes data from the Lifetime assessment obtained at Screening or Baseline/Week 0. The analysis period ‘Recent history’ includes data from the Past 6 Months assessment obtained at Screening or Baseline/Week 0. If there are multiple assessments within an analysis period/study phase, results will be derived as the worst-case value (i.e., an answer of ‘yes’ for the category) for that analysis period/study phase.

In addition, the number and percentage of participants with the following post-baseline events will be presented ([Nilsson et al., 2013](#)) by study phase (open-label treatment phase and open-label extension period) using the SAF. Note: In these definitions, a category of 0 is assigned to a participant without suicidal ideation (i.e., a ‘no’ answer to all suicidal ideation categories).

- Worsening suicidal ideation compared to recent history: An increase in the maximum suicidal ideation category at any time post-baseline from the maximum suicidal ideation category during pre-treatment recent history.
- Worsening serious suicidal ideation compared to recent history: An increase in the maximum suicidal ideation category to 4 or 5 at any time post-baseline from not having serious suicidal ideation (categories of 0-3) during pre-treatment recent history.

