- Emergence of serious suicidal ideation compared to recent history: A maximum suicidal ideation category of 4 or 5 at any time post-baseline from no suicidal ideation (category 0) during pre-treatment recent history.

- Improvement in suicidal ideation at last on-treatment measurement compared to recent history: A decrease in suicidal ideation score at last on-treatment measurement from pre-treatment recent history.
- Emergence of suicidal behavior compared to all prior history: The occurrence of suicidal behavior (categories 6-10) at any time post-baseline from not having suicidal behavior (categories 6-10) prior to treatment (includes “lifetime” and any other assessments prior to treatment taken prior to treatment).

A participant can only be counted once within a given category; however, a participant can be counted in more than one category. Suicidal ideation and behavior data will be listed. Detailed answers to C-SSRS items will be listed separately for participants with any suicidal ideation at any time post-baseline (i.e., a ‘yes’ answer to at least one of the five suicidal ideation questions at any time post-baseline) and for participants with any suicidal behavior at any time post-baseline (i.e., a ‘yes’ answer to at least one of the five suicidal behavior questions at any time post-baseline). Additional details are provided in the TFL Shells document.

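### A pre-dose Day 1 C-SSRS on neither a Lifetime nor a Past 6 Months form would be counted in the open-label treatment phase occurrence rows, although the SAP treats it as baseline

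*SAP*

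**What the plan says.** **Phase.** SAP 2.1.1 (Open-label treatment phase/extension period) says that "data occurring from Study Day 1 through the Month 18 interim analysis data cut-off will be considered as part of the open-label treatment phase". The data types it names are given as examples, so the rule reaches the C-SSRS. Study Day 1 "is defined as the date of the first dose of ofatumumab for ofatumumab-treated participants"; no clock time is involved.

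**Baseline.** SAP 2.1.1 (Baseline) takes the last non-missing assessment on or before the first-dose date. Post-baseline means "all assessments obtained after the date of the first dose of ofatumumab for ofatumumab-treated participants".

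**C-SSRS analysis.** SAP 2.7.4.3 has three outputs that matter here.
- Occurrence rows, by all prior history, recent history, treatment phase, extension and overall. The first is "Each of the 10 individual suicidal ideation and behavior categories (during the analysis period/study phase of interest"). The same qualifier applies to the other rows, and no post-baseline filter is stated. "If there are multiple assessments within an analysis period/study phase, results will be derived as the worst-case value".
- Worsening, emergence and improvement rows, where "the number and percentage of participants with the following post-baseline events will be presented".
- Detailed listings: "Detailed answers to C-SSRS items will be listed separately for participants with any suicidal ideation at any time post-baseline", with a matching rule for behaviour.

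The two history periods are described by form. Recent history "includes data from the Past 6 Months assessment obtained at Screening or Baseline/Week 0"; all prior history is described in the same way for the Lifetime form.

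**C-SSRS schedule.** Protocol Table 8-1 marks the scale at both Screening and Baseline/Week 0. Its footnote 15 and protocol 8.4.3 require a first administration at one of these two visits and then one at each later on-site visit. Protocol 6.3.2 has the first injection given on site at Baseline/Week 0 and places dosing after that day's assessments.

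**The concern.** A scale administered before the first injection cannot reflect exposure to ofatumumab. Read literally, the phase rule still reports a positive answer from that administration under a treatment-phase heading. The same record is baseline under another paragraph of SAP 2.1.1. For suicidal behaviour it also belongs to the pre-treatment reference, because the emergence-of-behaviour row in SAP 2.7.4.3 counts other pre-treatment assessments as prior history. One record would then be pre-treatment in one row and treatment-phase in another.

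At stake is the accuracy of low-frequency safety counts, where one participant can be the whole count, and agreement between outputs. A participant positive only on Day 1 would appear in a treatment-phase row but not in the detailed post-baseline listing that a reader would turn to next.

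**Working it through.** The plan gives no figure for this point, so the check is one of classification, followed by the size per participant.

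**1. When the record exists.** With a first C-SSRS at Screening, the Baseline/Week 0 visit is a later on-site visit and the scale is repeated. Under protocol 6.3.2 it comes before the injection. If the scale is first given at Baseline/Week 0, that record carries the history forms and there is no separate repeat.

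**2. How each record is classified.**

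| C-SSRS record | Phase rule, SAP 2.1.1 | Baseline rule, SAP 2.1.1 |
|---|---|---|
| Screening | before the phase | on or before first-dose date |
| Day 1, pre-dose | open-label treatment phase | on or before first-dose date |
| Week 1 | open-label treatment phase | post-baseline |
| Month 18 | open-label treatment phase | post-baseline |

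Only the Day 1 record is classified in conflict.

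**3. Whether other text moves it.**
- The history periods in SAP 2.7.4.3 can take a Lifetime or Past 6 Months form completed on Day 1. They do not mention any other form, and there is no baseline period.
- SAP Table 3 maps study day 1 or earlier to baseline, but its readable title does not list the C-SSRS. The document history records that the C-SSRS was removed from that table.
- The time-of-dose rule under Multiple assessments in SAP 2.4.1.1 selects a baseline value. It does not assign a phase.
- The Screening paragraph of SAP 2.1.1 labels pre-dose procedures as screening. It creates no exception to the phase rule.

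**4. Rows affected.** 10 individual categories + 3 any-ideation/any-behaviour rows + 1 non-suicidal self-injury row = 14 occurrence rows in the treatment-phase column, and in an overall column if that is built from the phases.

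**5. When a row changes.** Table 8-1 schedules the C-SSRS at Baseline, Weeks 1, 2 and 4, and Months 3, 6, 12 and 18: 8 administrations, 7 of them after the first-dose date. Under the worst-case rule a row is overstated only for a participant who is positive on Day 1 and negative at all 7 later administrations and at any unscheduled one.

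**6. Size.** With a safety set of 118 (the planned enrolment, taken as an assumption), k such participants add k/118 to a row: 1/118 = 0.85, 2/118 = 1.69 and 5/118 = 4.24 percentage points.

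**7. How often.** The documents give no rate. For an assumed share p of participants with the Day 1-only pattern, the expected number is 118p and the chance of at least one is 1 − (1 − p)^118.

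| Assumed p | Expected number | Chance of at least one |
|---|---|---|
| 0.25% | 0.295 | 25.6% |
| 0.5% | 0.59 | 44.6% |
| 1% | 1.18 | 69.5% |
| 2% | 2.36 | 90.8% |

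This table only restates the assumed rates and is not evidence that the pattern will occur.

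**The case against.** **The triggering record is not certain to exist.** No text names the form used on Day 1 after a Screening administration. The either/or wording of footnote 15 and protocol 8.4.3 also allows the two marks in Table 8-1 to be read as alternatives. The SAP expects history data from either visit, and if the history form is completed on Day 1 the problem does not arise. This stands, and it is why the point is conditional. The requirement for every later on-site visit nevertheless supports a Day 1 repeat after Screening.

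**Protocol 12.5.2 limits safety summaries to on-treatment data, apart from baseline data.** A programmer could rely on this to leave out a pre-dose record. The intent is clear and favours the fix. But the section gives no pre-dose split for Day 1, while the SAP has an explicit date rule that says otherwise.

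**The TFL Shells may settle it.** SAP 2.7.4.3 refers further detail to them. This stands and cannot be checked here.

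**The consequence is slight.** No hypothesis is tested, all ideation and behaviour data are listed, and nothing requires the detailed listings to match the phase rows. This also stands and sets the severity.

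A reader might infer that the worsening and emergence counts are inflated too, or that a safety signal is hidden. The documents do not support either inference. Those rows are confined to post-baseline events, so the Day 1 record cannot be one, and the error in the occurrence rows can only over-count.

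**Conclusion.** The point holds in conditional form and is minor. If the history forms are completed at Screening and the Day 1 repeat uses neither of them, following SAP 2.1.1 as written places a pre-dose baseline record in the treatment-phase occurrence rows of SAP 2.7.4.3. The overstatement is 0.85 percentage points of a row per participant whose only positive answer in the phase is on Day 1, assuming 118 in the safety set. The number of such participants is unknown and may be zero. The primary endpoint is not affected. Confidence is medium, because the Day 1 form is unnamed and the Shells are unseen.

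A reader might also infer that the Day 1 repeat should be added to the recent-history reference for ideation, as is done for behaviour. The SAP does not say whether it enters that reference, and the finding does not call for it. Adding a record can only raise the reference maximum or leave it unchanged, so it can only lower the worsening and emergence counts or leave them unchanged. That would trade away sensitivity in the signal-detecting rows to correct a descriptive one.

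**What to change.** Add one sentence to SAP 2.7.4.3: for the C-SSRS occurrence rows, the open-label treatment phase, and the on-study part of overall, include only post-baseline assessments, meaning those dated after the first dose; this overrides the Study Day 1 rule in Section 2.1.1. Leave the recent-history ideation reference as it is.

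The cost is that sentence and a small programming change, with no new data. If the Shells already do this, the sentence brings the SAP into line with them.

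The downside is that a C-SSRS done after the injection on Day 1, contrary to protocol 6.3.2, would leave the treatment-phase rows and appear only in the general listing. A pre-dose Day 1 answer on another form would also leave those rows. It would remain in the general listing and, for behaviour, in the pre-treatment reference.
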